6. HYPOTHESES AND DECISION RULES

6.1. Statistical Hypotheses

This study is exploratory in nature, no pre-specified hypothesis tests are to be performed.

7. ANALYSIS SETS

7.1. Full Analysis Set

In general, the full analysis set is comprised of all randomized subjects. This population of subjects is not applicable for this study. Analysis sets for safety, PK, and pharmacodynamic data are defined in Sections 7.3, 7.4 and [7.5](#).

7.2. 'PER PROTOCOL' Analysis Set

n/a.

7.3. Safety Analysis Set

The Safety Analysis Set consists of all patients who receive any amount of dose of study medication. The Safety Analysis Set will be used for all analyses.

7.4. Pharmacokinetic (PK) Analysis Set

7.4.1. PK Concentration Analysis Set

The pharmacokinetic (PK) concentration population is defined as all enrolled subjects treated who have at least 1 measurable (>LLOQ) concentration value.

7.4.2. PK Parameter Analysis Set

The PK parameter analysis population is defined as all subjects randomized and treated who have at least 1 of the PK parameters of interest.

7.5. Pharmacodynamic (PD) Analysis Set

The PD population is defined as all subjects randomized and treated who have at least 1 measurable plasma concentration of studied medication (PF-06293620), and:

- Fasting plasma glucose,
- Fasting glucagon,
- Fasting GLP-1,
- Glucose, insulin, C-peptide, GLP-1 after 4 hour mixed meal tolerance test (MMTT)
- 1,5-anhydroglucitol,
- fructosamine,
- HbA1c,
- AUC0-24hr of glucose,
- mean daily blood glucose levels (from fingerstick).

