9.6. Exploratory Analyses

Exploratory analyses will be conducted for SAD and MAD, respectively. The individual subject's change and percentage change from baseline for PD biomarkers over the period of the study will be tabulated by individual subject. The mean change from baseline values over time per dose group will also be tabulated. Data will be presented in tabular and/or graphical format and summarized descriptively. Placebo subjects will be pooled across all dose cohorts for the respective stages of the study, ie, SAD placebo subjects and MAD placebo subjects. To explore the treatment effect¹⁶, the mean change and percentage change from baseline over time with active treatment will be compared to the mean change and percent change from baseline over time with placebo treated subjects. Descriptive statistics on change and percentage change from baseline in fasting plasma glucose, post prandial glucose, insulin, C-peptide and glucagon AUC after mixed meal tolerance test (MMTT, 4 hr), 24-hr glucose profile (finger-stick), HbA1c, fructosamine, 1,5-anhydroglucitol; fasting

glucagon, total and active GLP-1 will be provided separately for each treatment and the pooled placebo group.

Exploratory PK/PD analyses may be conducted on relevant safety and PD endpoints as permitted by the data.

Data listings will be produced by study portion (SAD or MAD), subject, dose cohorts, visit date, and time.

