10. STATISTICAL METHODOLOGY AND STATISTICAL ANALYSES

10.1. Statistical Methods

- All analyses will be presented by dose group.
- Placebo subjects will be pooled across cohorts for analysis and presentation purpose.
- Continuous data will be summarized using descriptive statistics: number of subjects (n), mean, standard deviation, standard error, median, minimum and maximum. 90% confidence intervals (CI) may be provided for pharmacodynamics endpoints.
- Categorical data will be described using frequencies and percentages. The denominator for all percentages will be the number of subjects for whom there are data in the cohort/treatment group within the analysis set of interest, unless otherwise specified. Counts of subjects with missing data will be presented if applicable.
- All data will be presented in listings. Data that will only be listed (not summarized) are specified in the analysis section.

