10.2.3.3. Pharmacokinetic parameters

Actual PK sampling times will be used in the derivation of PK parameters.

If a PK parameter cannot be derived from a subject's concentration data, the parameter will be coded as NC (ie not calculated). (Note that NC values will not be generated beyond the day that a subject discontinues.)

In summary tables, statistics will be calculated by setting NC values to missing; and statistics will not be presented for a particular treatment if more than 50% of the data are NC. For statistical analyses (ie analysis of variance), PK parameters coded as NC will also be set to missing.

If an individual subject has a known biased estimate of a PK parameter (due for example to an unexpected event such as coughing during or immediately after inhalation before all of the drug is absorbed by the body), this will be footnoted in summary tables and will not be included in the calculation of summary statistics.

To assess the pharmacokinetics of PF-06293620, PK parameters will be listed and summarized for subjects in the PK analysis set (as defined in [Section 7](#)). Missing values will be handled as detailed above.

The PK parameters to be summarized by treatment are outlined in Table 8.

Table 8. SAD and MAD Cohorts PK Parameters:

Parameter	Summary statistics
SAD Cohort	
AUC _{inf} , AUC _{last} , C _{max} , V _z /F, V _{ss} , CL/F, CL, AUC _{inf} (dn), AUC _{last} (dn), C _{max} (dn)	N, arithmetic mean, median, cv%, standard deviation, minimum, maximum, geometric mean, geometric CV%.
T _{max}	N, median, minimum, maximum.
t _{1/2}	N, arithmetic mean, median, cv%, standard deviation, minimum, maximum.
MAD Cohorts	
AUC _τ , C _{max} , C _{min} , CL/F, C _{av} , V _z /F, R _{ac} , R _{ac,Cmax} , AUC _τ (dn), C _{max} (dn), C _{min} (dn)	N, arithmetic mean, median, cv%, standard deviation, minimum, maximum, geometric mean, geometric CV%.
T _{max}	N, median, minimum, maximum.
t _{1/2}	N, arithmetic mean, median, cv%, standard deviation, minimum, maximum.

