10.2.4. Pharmacodynamic Analyses

PD biomarker data will include fasting plasma glucose, fasting glucagon, fasting GLP-1, 24-hr glucose profile (finger-stick), mean daily glucose profile, HbA1c, fructosamine, 1,5-anhydroglucitol, and glucose, insulin, C-peptide, glucagon and GLP-1 AUC after mixed meal tolerance test (MMTT, 4 hr). The relationship between changes in the values of these biomarkers with the pharmacokinetics of PF-06293620 may be explored. Exploratory PK/PD modeling may be performed if visual examination of the data is suggestive of a relationship.

The change and percentage change from baseline for PD biomarkers over the period of the study will be tabulated by treatment. The mean change from baseline values over time per cohort will also be tabulated. Data will be presented in tabular and graphical format and summarized descriptively. Descriptive statistics on change from baseline in fasting plasma glucose, fasting glucagon, fasting GLP-1, 24-hr glucose profile (finger-stick), HbA1c, fructosamine, 1,5-anhydroglucitol, and glucose, insulin, C-peptide, glucagon and GLP-1 AUC after mixed meal tolerance test (MMTT, 4 hr), and lipid parameters will be provided separately for each treatment and the pooled placebo group. The mean change from baseline over time with active treatment may be compared to the mean change from baseline over time with pooled placebo treated subjects using MMRM analysis with treatment as fixed effect, subject as a random effect, and baseline value as covariate adopting unstructured covariance structure. Figures of absolute values, change from baseline, and percentage change from baseline over time may be produced if needed.

The relationship between changes in the values of these biomarkers with the pharmacokinetics of PF-06293620 will be explored. Exploratory PKPD modeling may be performed if visual examination of the data is suggestive of a relationship.

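### The PD analysis set in SAP 7.5 shuts out every placebo subject, although SAP 10.2.4 and protocol 9.6 call for pooled-placebo PD results

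*SAP*

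**What the plan says.** SAP 7.5 defines the PD population as "all subjects randomized and treated who have at least 1 measurable plasma concentration of studied medication (PF-06293620"), joined by a conjunction to a list of PD measures. Nothing in the section treats placebo differently.

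Other parts of the plan need placebo subjects in the PD results:

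- SAP 10.2.4 says descriptive statistics on PD change from baseline "will be provided separately for each treatment and the pooled placebo group". It adds that mean change on active treatment "may be compared to the mean change from baseline over time with pooled placebo treated subjects", using an MMRM.
- Protocol 9.6, which covers the PD biomarkers, says "Placebo subjects will be pooled across all dose cohorts for the respective stages of the study", and plans to compare active with placebo on change from baseline.
- SAP 10.1 sets the general rule: "Placebo subjects will be pooled across cohorts for analysis and presentation purpose".

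On which set governs the PD analyses, the SAP gives two signals. Section 7.1 says "Analysis sets for safety, PK, and pharmacodynamic data are defined in Sections 7.3, 7.4 and" 7.5. Section 7.3 says "The Safety Analysis Set will be used for all analyses". Section 10.2.4 names no set.

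**The concern.** A condition that requires measurable drug suits a PK or exposure-response set. Used as the entry rule for a placebo-controlled PD comparison, it removes the control arm. If the PD tables are built on the 7.5 set, the pooled-placebo column in SAP 10.2.4 is empty and the optional MMRM contrast cannot be fitted. If they are built on the Safety Set under 7.3, placebo stays in and the 7.5 definition is never used. Two programmers could each cite the SAP and deliver different PD tables. The sponsor team is unblinded in this study (SAP section 3), so the choice should be fixed in writing and not made while the outputs are being produced.

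PD also carried some weight in the design. SAP section 3 says the 75 mg cohort was enlarged for further PD evaluation, and SAP Table 2 gives it 16 active and 4 placebo subjects, against 8 and 2 in each of the other two MAD cohorts.

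**Working it through.** The check is mainly logical; the arithmetic only sizes it.

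**1. Can a placebo subject satisfy SAP 7.5?**

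- The entry condition is at least one measurable PF-06293620 concentration. SAP 7.4.1, the adjacent PK definition, takes measurable to mean above the lower limit of quantification.
- Placebo subjects are given no PF-06293620.
- Protocol 5.2 has their PK samples drawn to protect the blind but not routinely analysed, so they would normally have no concentration result at all.
- SAP 7.7 reports subjects as treated. A placebo-assigned subject given active drug in error would count as active and would not restore a control.

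Placebo subjects eligible by design: 0.

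**2. How many subjects does that affect?**

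| Part | Source | Active | Placebo | Total |
|---|---|---|---|---|
| SAD | SAP Table 1, 5 cohorts of 6 + 2 | 5 × 6 = 30 | 5 × 2 = 10 | 40 |
| MAD | SAP Table 2 | 8 + 16 + 8 = 32 | 2 + 4 + 2 = 8 | 40 |
| Both | | 62 | 18 | 80 |

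The totals reproduce the approximately 40 + 40 = 80 in protocol 3.2. Placebo shares are 10/40 = 25% in SAD, 8/40 = 20% in MAD and 18/80 = 22.5% overall. Under 7.5 the placebo counts become 0 of 10 and 0 of 8, and the PD set holds at most 62 subjects. Without the concentration condition, or with it limited to PF-06293620 recipients, the set can hold up to 80, of whom 18 are placebo.

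**3. Does other text resolve it?**

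- SAP 7.3, read literally, would keep placebo in. But 7.1 points to a separate definition for PD data, and the PK section does not follow 7.3 literally either: in SAP 10.2.3.3, "PK parameters will be listed and summarized for subjects in the PK analysis set".
- Protocol 9.4 defines no PD population, so 7.5 is the only definition available.
- SAP section 2 says the SAP supersedes the protocol's statistical considerations, so protocol 9.6 cannot be relied on to override 7.5.

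**The case against.** The strongest reply is that the SAP has a default that keeps placebo in. Section 7.3 assigns the Safety Set to all analyses, the PK sections depart from that default by naming their own set, and 10.2.4 names none, so the default could apply to PD. Section 7.1 says where the sets are defined, not which analysis uses which. Nothing in SAP section 10 invokes the 7.5 set, and the subject evaluation groups in 10.2.2 mention only PK and safety. The intention to show placebo is stated several times, so an empty placebo column would be noticed at once and would not silently bias a result. PD is exploratory, no hypothesis is tested and the MMRM is optional.

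Much of this is fair as to consequence. The intention is clear, the error would probably be caught, and the stakes are limited. It does not make the text consistent. Applying the default means treating the SAP's only PD definition as having no purpose; applying the definition means failing a mandatory output in 10.2.4. A programmer who adds placebo does the sensible thing by departing from 7.5.

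Three smaller points stand. SAP 10.1 is a general pooling rule and does not itself require PD summaries; the specific requirements are in 10.2.4 and protocol 9.6. The figure of 18 in 80 shows the reach of the rule, not a shift in any estimate. It also combines planned SAD numbers with tabulated MAD numbers.

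**Conclusion.** The concern holds. SAP 7.5 as written admits 0 of 18 placebo subjects, which contradicts the pooled-placebo PD statistics required by SAP 10.2.4 and the comparison planned in protocol 9.6. SAP 7.3 adds a second inconsistency and does not cure the first. This should be corrected before the PD outputs are programmed.

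The effect is confined to the exploratory PD results. The primary safety and immunogenicity analyses and the secondary PK analyses do not depend on the 7.5 set.

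The counts assume the cohort sizes in SAP Tables 1 and 2 and ignore missing data and replacements. Actual SAD numbers probably differ: protocol Table 1 already shows 9 placebo subjects among 36 randomized at the May 2015 cutoff, when the table held Cohorts 1 to 4 only, so the 2 placebo subjects planned for Cohort 5 would give 11. SAD subjects may re-enter in MAD, so 80 need not be 80 different people. A MAD placebo subject with residual drug from an earlier active SAD dose is a theoretical exception and would not supply a control group. None of this changes the conclusion.

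**What to change.** - **SAP 7.5:** define the PD set as all randomized and treated subjects, active or placebo, with a baseline and at least one post-baseline value for the PD endpoint being analysed. The smallest sufficient change is to apply the concentration condition only to subjects who received PF-06293620.
- **Exposure-response work:** keep the measurable-concentration condition there, where it belongs.
- **SAP 10.2.4:** name the PD set as the analysis set.
- **SAP 7.3:** limit the sentence on use of the Safety Set to safety analyses. Make this change together with the one in 7.5, because the present sentence is the only text that assigns placebo subjects to a usable set for PD.

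The cost is wording in three SAP sections, with no new data. SAP 7.8 already foresees an update before database lock, so the changes can go into that version.

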7.6. Other Analysis Sets

N/A.

7.7. Treatment Misallocations

All analyses will be performed on an “as-treated” basis and will not include data from subjects who are randomized but not treated.

If a subject takes a treatment that is not consistent with the treatment they are randomized to, subjects will be reported under the treatment that they actually received for all safety, PK and pharmacodynamic analyses, where applicable.

7.8. Protocol Deviations

Protocol deviations will be defined and this analysis plan updated before database lock.

7.8.1. Deviations assessed prior to randomization

At Screening, the investigator will assess subjects against the inclusion and exclusion criteria as set out in Sections 4.1 and 4.2 of the protocol.

7.8.2. Deviations assessed post-randomization

A full list of protocol deviations for the study report will be compiled prior to database closure. Any significant deviation from the protocol will be reviewed prior to database closure and a decision taken regarding evaluation for each analysis population.

8. ENDPOINTS AND COVARIATES

In general, Baseline is defined as the last available data prior to first study medication administration except for the following endpoints the Baseline is defined in Table 3.

Table 3. Baseline definition

Measurement	SAD	MAD
Fasting Weight	Mean of (Day -1, 1)	Mean of (Day -2, -1 and 1)
Temperature	Mean of (Day -1, 1)	Mean of (Day -2, -1 and 1)
Pulse Rate	Mean of (Day -1, 1)	Mean of (Day -2, -1 and 1)
Systolic Blood Pressure	Mean of (Day -1, 1)	Mean of (Day -2, -1 and 1)
Diastolic Blood Pressure	Mean of (Day -1, 1)	Mean of (Day -2, -1 and 1)
Fasting Plasma Glucose	Mean of (Day -1, 1)	Day 1 pre-dose
Fasting Glucagon	Mean of (Day -1, 1)	Day 1 pre-dose
Fasting GLP-1	Mean of (Day -1, 1)	Day 1 pre-dose

For triplicate ECG and vital signs readings, baseline is defined as the mean value of triplicate measurements prior to first study medication administration.

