- Weight measure in gown, undergarments and socks (or in comparable standard garments used by the CRU) while fasting and empty bladder. Height measured with wall-mounted stadiometer at screening only in stocking feet and carried forward.
- Vital signs: blood pressure, pulse, temperature. Only blood pressure should be collected in triplicate. On dosing days obtain at prior to dose and at 1, 2, and 4 hours after dosing.
- Screening labs include FSH in women only, TSH, C-peptide, HIV, hepatitis B surface antigen, hepatitis B core antibody, hepatitis C antibody.
- Subjects will continue to be monitored, at approximately 1-3 month intervals, for up to 9 months beyond the last scheduled visit, if necessary, for elevated glucagon levels and/or presence of anti-PF-06293620 antibodies.
- Samples for MMTT assessment should be collected prior to the MMTT (0 minutes/fasting) and after the start of the liquid meal at 15, 30, 60, 120, 180 and 240 minutes. Blood glucose, C-peptide, insulin, glucagon and GLP-1 will be measured at all timepoints.

- f. Fingersticks with glucometer measurements to be taken before breakfast (fasting), 2-hr post-breakfast, before lunch, 2-hr post-lunch, before dinner, 2-hr post-dinner, prior to snack (between 9 and 10 PM) and then at 0300 and before breakfast (fasting) the following days (Day 1, Day 9 and Day 65). Days 9 and 65 are done as outpatient, at home.
- g. PK: on dosing days, PK sample will be collected at hours 0 (predose), 1 and 4 hours post dose.
- h. Perform injection site assessment immediately after injection, 15 minutes, 30 minutes, 1 hour, and 2 hours post administration. Additional assessments should be performed as needed after the last assessment of 2 hrs post-dose on dosing days.
- i. Subject to be questioned about compliance with metformin.
- j. Triplicate ECG: All ECG will be submitted to Central ECG vendor for independent review. On dosing days, collect triplicate ECG prior to study drug administration (pre-dose) and 1, 2, and 4 hours after dosing.
- k. Fasting plasma glucose, glucagon and GLP-1 are not collected on days when MMTT are performed – these analytes will be captured as part of the MMTT Time 0/fasting timepoint.

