6.2.2. Day-1 - SAD

On Day -1, after an overnight fast of at least 10 hours, and the following procedures will be completed:

- Review medical history including recreational drug, alcohol and tobacco use, and medication history.
- Conduct limited physical exam of the skin, heart, lungs, abdomen and extremities by trained medical personnel at the investigator site.
- Collect fasting weight and triplicate waist circumference.
 - To measure waist circumference, use a spring-loaded tape measure, and starting at the top of the hip bone, bring it all the way around, level with the navel. Tape measure should not be too tight and parallel with the floor. Instruct subject to not hold their breath. Measurement should not include navel.
- Obtain temperature and supine pulse and supine triplicate blood pressure. Blood pressure will be the only vital sign collected in triplicate.
- Collect blood samples for the following:
 - Fasting lipid profile;
 - HbA1c;
 - Fructosamine;
 - 1,5-anhydroglucitol;
 - ADA;
 - Banked Specimen (Pharmacogenomics).
- Collect adverse events.
- Question subjects regarding metformin compliance.
- Obtain fingerstick glucose before breakfast (before MMTT).
- Before MMTT, collect 0 minute fasting timepoint blood samples for FPG, C-peptide, insulin, glucagon and GLP-1 (all cohorts).

- Administer MMTT in AM; begin sample collection (glucose, C-peptide, insulin, glucagon and GLP-1):
 - 15 minutes from start of meal (first sample collected 5 minutes post meal; the liquid should take 10 minutes to consume; See [Section 7.4.1.2](#));
 - 30 minutes;
 - 60 minutes;
 - 120 minutes;
 - 180 minutes;
 - 240 minutes.
- Obtain fingerstick glucose measurements 2 hr post- breakfast, before lunch, 2-hr post-lunch, before dinner, 2-hr post-dinner, prior to snack (between 9 and 10 PM).
- Initiate continuous cardiac telemetry at least 12 hours prior to dosing on Day 1.
- Randomize subject to study treatment.

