6.3.3. Day -1 MAD

On Day -1, after an overnight fast of at least 10 hours, the following procedures will be completed:

- Assess symptoms by spontaneous reporting of adverse events and by asking the subjects to respond to a non-leading question such as “How do you feel?”
- Review medical history
- Assess patency of peripheral IV (PIV)/heplock, in accordance with site policies,
 - If no longer patent remove and insert a new PIV/heplock in accordance with site policies. Allow subject to rest at least 1 hour prior to obtaining vital signs.
- Obtain blood sample at approximately 03:00 AM and 07:30 AM (immediately prior to breakfast) to complete the mean daily glucose profile.
- Obtain temperature, supine pulse and triplicate supine blood pressure.
- Complete 24 hour ambulatory blood pressure monitoring.

- NOTE: Before proceeding with any other Day -1 assessments, immediately upload the Day -2 Ambulatory blood pressure monitoring (ABPM) data to the vendor to determine if the data passes vendor technical quality control (QC). If the data fails technical QC, immediately restart/repeat the ABPM on Day -1 to ensure a baseline/pre-dose dataset is obtained. Then start the remaining Day -1 procedures.
- Conduct limited physical exam of the skin, heart, lungs, abdomen and extremities by trained medical personnel at the investigator site.
- Collect fasting weight and triplicate waist circumference.
 - To measure waist circumference, use a spring-loaded tape measure, and starting at the top of the hip bone, bring it all the way around, level with the navel. Tape measure should not be too tight and parallel with the floor. Instruct subject to not hold their breath. Measurement should not include navel.
- Collect blood samples for the following:
 - Fasting serum chemistry;
 - Hematology;
 - Fasting lipid profile;
 - Apo B;
 - HbA1c;
 - Fructosamine;
 - 1,5-anhydroglucitol;
 - ADA;
 - Banked Specimen (Pharmacogenomics).
- Obtain fingerstick glucose before breakfast (fasting) before MMTT.
- Before MMTT, collect 0 minute fasting timepoint blood sample for FPG, C-peptide, insulin, glucagon and GLP-1 (all cohorts).
- Administer MMTT in AM; begin sample collection (glucose, C-peptide, insulin, glucagon and GLP-1):
 - 15 minutes from start of meal (first sample collected 5 minutes post meal; the liquid should take 10 minutes to consume; See **Section 7.4.1.2**);

- 30 minutes;
- 60 minutes;
- 120 minutes;
- 180 minutes;
- 240 minutes.

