6.3.4. Day 1 - MAD

On Day 1, after an overnight fast of at least 10 hours, the following procedures will be completed **Prior to dosing**:

- Obtain finger-stick glucose measurement at 0300.
- Assess symptoms by spontaneous reporting of adverse events and by asking the subjects to respond to a non-leading question such as “How do you feel?”
- Assess patency of peripheral IV (PIV)/heplock, in accordance with site policies.
 - If no longer patent remove and insert a new PIV/heplock in accordance with site policies. Allow subject to rest at least 1 hour prior to obtaining vital signs and initiating 24 hour ambulatory blood pressure monitoring.
- Collect triplicate 12-Lead ECG.
- Collect temperature, supine pulse and triplicate supine blood pressure.
- Obtain finger-stick glucose measurement prior to breakfast (fasting).
- Obtain fasting weight.
- Collect a blood sample for pharmacokinetic analysis (pre-dose).
- Collect blood samples for the following:
 - Hematology;

- Fasting clinical chemistry;
- Coagulation panel, amylase and lipase.
- Collect blood for FPG, fasting glucagon and fasting GLP-1.
- Collect urine for urinalysis (clean catch, midstream).
- Initiate 24 hour ambulatory blood pressure monitoring (at least 1 hour prior to study drug administration).
 - Placement of cuff must not be on the same arm as the PIV.
- Administer the study medication (see **STUDY TREATMENTS** and **Administration Sections**).

After dosing, the following procedures will be completed:

- Assess temperature, supine pulse rate and triplicate supine blood pressure at 1, 2, and 4 hours after dosing. Blood pressure is the only vital sign to be collected in triplicate.
- Obtain triplicate 12-lead ECG measurements at 1, 2, and 4 hours after dosing.
- Collect blood samples for pharmacokinetic analysis at 1 and 4 hours following dosing.
- Injection site assessment immediately after injection at: 15 and 30 minutes, 1, and 2 hours post administration. Additional assessments should be performed as needed after the last assessment of 2 hrs post-dose on dosing days.
- Record concomitant medication.
- Assess symptoms by spontaneous reporting of adverse events and by asking the subjects to respond to a non-leading question such as “How do you feel?”
- Question subject on metformin compliance.

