6.3.21. Day 64 (± 1) - MAD

On Day 64, after an overnight fast of at least 10 hours, the following procedures will be completed:

- Assess symptoms by spontaneous reporting of adverse events and by asking the subjects to respond to a non-leading question such as “How do you feel?”
- Assess patency of peripheral IV (PIV)/heplock, in accordance with site policies,
- If no longer patent remove and insert a new PIV/heplock in accordance with site policies. Allow subject to rest at least 1 hour prior to obtaining vital signs.
- Complete 24 hour blood pressure monitoring.
 - NOTE: Before proceeding with any other Day 64 assessments, immediately upload the Day 63 ABPM data to the vendor to determine if the data passes vendor QC. If the Day 63 data fails technical QC, immediately restart/repeat the ABPM on Day 64 to ensure a complete dataset is obtained. Then perform the remaining Day 64 procedures. If the 24 hour ambulatory blood pressure monitoring cannot be repeated on Day 64 please contact the sponsor to discuss alternative times.
- Obtain fasting weight.

- Obtain temperature, supine pulse rate and triplicate supine blood pressure. Blood pressure will be the only vital sign collected in triplicate.
- Collect blood samples for:
 - Liver Function Test: ALT, AST, GGT, lactate dehydrogenase (LDH), alkaline phosphatase, total bilirubin, indirect bilirubin, direct bilirubin and creatine kinase;
 - Fasting lipid profile;
 - Apo B;
 - Pharmacokinetic analysis;
 - Obtain fingerstick glucose before breakfast (before MMTT);
 - Prior to MMTT, collect the time 0 minute fasting blood samples for FPG, C-peptide, insulin, glucagon and GLP-1;
 - Administer MMTT in AM. Collect samples (glucose, C-peptide, insulin, glucagon and GLP-1) at:
 - 15 minutes (5 minutes after fluid meal is consumed which requires 10 minutes; See **Section 7.4.1.2**);
 - 30 minutes;
 - 60 minutes;
 - 120 minutes;
 - 180 minutes;
 - 240 minutes.
 - Obtain fingerstick glucose measurements 2 hr post- breakfast, before lunch, 2-hr post-lunch, before dinner, 2-hr post-dinner, prior to snack (between 9 and 10 PM).
 - Afternoon, evening, 0300 (Day 65) and before breakfast (Day 65) fingersticks will be performed after discharge from the CRU.
 - Record concomitant medications.
 - Question subject on metformin compliance.
 - Remove PIV/heplock prior to discharge.

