9.4. Pharmacodynamic Analysis

PD biomarker data will include fasting plasma glucose, fasting glucagon, fasting GLP-1, 24-hr glucose profile (finger-stick), HbA1c, fructosamine, 1,5-anhydroglucitol, post prandial glucose, insulin, C-peptide, glucagon and GLP-1 AUC after mixed meal tolerance test (MMTT, 4 hr) as well as mean daily glucose (MDG).

The relationship between changes in the values of these biomarkers with the pharmacokinetics of RN909 (PF-06293620) will be explored.

In order to minimize the impact of a single aberrant measurement to the baseline, where feasible, the baseline is defined as the average of at least two measurements prior to the first study drug administration as outlined in the statistical analysis plan.

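### SAP Table 3 uses Day 1 alone as the MAD baseline for fasting glucose, glucagon and GLP-1, although two pre-dose values are collected and protocol 9.4 asks for their average

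*SAP*

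**What the plan says.** Protocol 9.4 sets the default for pharmacodynamic markers: "where feasible, the baseline is defined as the average of at least two measurements prior to the first study drug administration", with the detail left to the SAP. The stated purpose is to limit the influence of one aberrant value.

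SAP section 8 takes the last value before first dosing as the general baseline, "except for the following endpoints the Baseline is defined in Table 3". For fasting plasma glucose that table reads "Fasting Plasma Glucose Mean of (Day -1, 1) Day 1 pre-dose", the first entry being SAD and the second MAD. The rows for fasting glucagon and fasting GLP-1 are identical. In the same MAD column, weight, temperature, pulse rate and blood pressure are averaged over Days -2, -1 and 1.

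The MAD procedures provide two pre-dose fasting values for each analyte:

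- **Day -1.** Protocol 6.3.3 collects all three at time 0 of the mixed meal tolerance test (MMTT). Note k of the MAD Schedule of Activities explains that no separate fasting sample is drawn on MMTT days because "these analytes will be captured as part of the MMTT Time 0/fasting timepoint".
- **Day 1, before dosing.** Protocol 6.3.4: "Collect blood for FPG, fasting glucagon and fasting GLP-1".

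**The concern.** The protocol's only condition for averaging is feasibility, and the samples needed are already scheduled. The SAP averages the equivalent samples in SAD but not in MAD, and does not say why.

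The baseline enters every MAD change and percent-change summary of these analytes. It is also the covariate if the mixed model for repeated measures (MMRM) is run, which SAP 10.2.4 leaves optional. The groups are small: SAP section 3, Table 2 gives 8 active subjects at 50 mg, 16 at 75 mg and 8 at 150 mg, with 2 + 4 + 2 = 8 pooled placebo. One poor baseline value therefore carries visible weight in a group mean, above all in percent change, where the baseline is the denominator.

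**Working it through.** The plan gives no figure tied to the baseline definition, so there is none to reproduce. The check has three parts.

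**1. Is the Day -1 sample of an acceptable kind?** SAD Day -1, which Table 3 does average, is also an MMTT time-0 sample (protocol 6.2.2), and the SAD schedule has no separate Day -1 fasting draw. In MAD, the post-dose fasting values on Days 8 and 64 are MMTT time-0 samples too (6.3.9 and 6.3.21; for Day 64: "Prior to MMTT, collect the time 0 minute fasting blood samples for FPG, C-peptide, insulin, glucagon and GLP-1"). MAD Day -1 follows a night of glucose-profile sampling, which SAD Day -1 does not, but so do the MAD fasting samples on Days 29 and 85 (6.3.13, 6.3.26). The type of sample does not explain the exclusion.

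**2. Precision.** The documents give no within-subject SD or correlation, so the inputs are assumptions. Take unit variances, let r be the correlation of each baseline value with a later value, and let q be the correlation between the two baseline values, with q ≥ r.

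- Change from baseline: variance 2(1 − r) with one value and 1.5 + q/2 − 2r with the mean of two. The relative reduction is (1 − q) / [4(1 − r)].
- Baseline-adjusted residual: variance 1 − r² with one value and 1 − 2r²/(1 + q) with the mean of two. The relative reduction is r²(1 − q) / [(1 + q)(1 − r²)].

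| r | q | Variance cut, change | Variance cut, adjusted |
|---|---|---|---|
| 0.5 | 0.99 | 0.5% | 0.2% |
| 0.5 | 0.95 | 2.5% | 0.9% |
| 0.5 | 0.9 | 5.0% | 1.8% |
| 0.5 | 0.75 | 12.5% | 4.8% |
| 0.5 | 0.5 | 25.0% | 11.1% |
| 0.3 | 0.9 | 3.6% | 0.5% |
| 0.7 | 0.9 | 8.3% | 5.1% |
| 0.9 | 0.9 | 25.0% | 22.4% |

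Simulation with 1,000,000 draws, run at four of these points, agreed to within 0.1 percentage point. For standard errors, a 25% variance cut is 1 − √0.75 = 13.4%, and a 5% cut is 1 − √0.95 = 2.5%.

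**3. One aberrant value, glucagon only.** Protocol 7.4.1.1 reports within-subject maximum-to-minimum ratios of 1.5 to 3.5 in six SAD placebo subjects. As a worst case, let Day 1 alone be off by a factor R, with Day -1 and the later value unchanged. The subject's spurious percent change is then:

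- Day 1 too high: 1/R − 1 with Day 1 alone; 2/(1 + R) − 1 with the mean of two.
- Day 1 too low: R − 1 with Day 1 alone; 2/(1 + 1/R) − 1 with the mean of two.

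| R | Day 1 is | One subject: Day 1 alone | One subject: mean of two | 8-subject mean: Day 1 alone | 8-subject mean: mean of two |
|---|---|---|---|---|---|
| 1.5 | high | −33.3% | −20.0% | −4.2 points | −2.5 points |
| 1.5 | low | +50.0% | +20.0% | +6.25 points | +2.5 points |
| 3.5 | high | −71.4% | −55.6% | −8.9 points | −6.9 points |
| 3.5 | low | +250.0% | +55.6% | +31.25 points | +6.9 points |

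The group shifts are the single-subject figures divided by 8. In the 16-subject 75 mg group they halve.

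**The case against.** The SAP has the authority to make this choice. Protocol 9.4 defers to it, protocol section 9 lets it modify protocol plans, and SAP section 2 promises to flag only substantial differences. This is therefore an unexplained departure from a default, not a breach of a rule.

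Day 1 pre-dose can also be defended on its merits. It matches the SAP's general rule and the ECG baseline, and it is a stand-alone fasting draw like most MAD post-dose fasting values; only Days 8 and 64 use MMTT time 0. That would be an arguable reason, but neither document gives it, and it does not fit with averaging the same kind of Day -1 sample in SAD.

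The objections on size largely stand. The 25% ceiling for change from baseline needs q = r, meaning that baselines one day apart correlate no better than values weeks apart. At r = 0.5 and q = 0.9 the standard error falls by only about 2.5% for change, and about 0.9% with baseline adjustment. The glucagon ratio spans all of a subject's visits (about 13 scheduled fasting values for a SAD subcutaneous subject), so it overstates a typical one-day deviation. SAP 10.1 also provides medians, ranges and listings, in which an aberrant subject would show. No hypothesis tests are planned, and no primary or secondary endpoint is touched.

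**Conclusion.** The point holds. The MAD baseline for these three analytes departs without explanation from the protocol's averaging default and from the SAD column, and feasibility cannot account for it.

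The reach is limited to precision and robustness on exploratory endpoints. The same definition applies to active and placebo subjects, so the comparison with placebo is not biased. The precision gain lies between almost nothing and 25% of the variance of change from baseline, depending on correlations that the documents do not report. The glucagon figures are an upper bound for a single bad value, not an expected effect.

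The precision result assumes that the two baseline values have similar variance and similar correlation with later values. If their correlations differ, say r₁ for Day 1 and r₂ for Day -1, the variance of change falls by (1 − q)/2 − (r₁ − r₂). Averaging then still helps unless Day 1 is the better predictor by more than (1 − q)/2, which is 0.05 at q = 0.9. Nothing in the documents suggests such a gap. The change is worth making because it costs almost nothing and follows the protocol's own default.

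**What to change.** In SAP Table 3, set the three MAD cells (fasting plasma glucose, fasting glucagon, fasting GLP-1) to the mean of the Day -1 MMTT time-0 value and the Day 1 pre-dose value, as in SAD. If one is missing, use the other. For glucose, state that the pre-breakfast samples of the Day -2 to Day -1 glucose profile do not enter this mean.

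If the sponsor has a reason to keep Day 1 alone, section 8 should state it and note the difference from protocol 9.4. That would remove the inconsistency but not recover the precision or robustness.

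The cost is three cells in one table, to be changed before database lock. No new samples or visits are needed.
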